[Part 2 of 2 of the document. The other parts are not shown.]

Weight (kg)	Dose	Frequency and/or Regimen	Total Daily Dose	Pharmaceutical form and route of administration
10-11.5	20 mg	b.i.d	40 mg	Dispersible tablet for oral suspension
11.6-17.5	30 mg	b.i.d	60 mg	Dispersible tablet for oral suspension
17.6-20.5	40 mg	b.i.d	80 mg	Dispersible tablet for oral suspension
20.6-24.5	50 mg	b.i.d	100 mg	Dispersible tablet for oral suspension
24.6-28.5	60 mg	b.i.d	120 mg	Dispersible tablet for oral suspension
28.6-32.5	70 mg	b.i.d	140 mg	Dispersible tablet for oral suspension
32.6-36.5	80 mg	b.i.d	160 mg	Dispersible tablet for oral suspension
36.6-40.5	90 mg	b.i.d	180 mg	Dispersible tablet for oral suspension
40.6-43.5	100 mg	b.i.d	200 mg	Dispersible tablet for oral suspension
43.6-47.5	110 mg	b.i.d	220 mg	Dispersible tablet for oral suspension
47.6-51.5	120 mg	b.i.d	240 mg	Dispersible tablet for oral suspension
51.6-55.5	130 mg	b.i.d	260 mg	Dispersible tablet for oral suspension
55.6-64.5	140 mg	b.i.d	280 mg	Dispersible tablet for oral suspension
≥64.6	150 mg	b.i.d	300 mg	Dispersible tablet for oral suspension

Please note that the new formulation (DT) applies to only the recommended doses, as the dose-escalation part of the study is already completed.

15.3 Appendix 3: Response Criteria for Solid Tumors (Not Neuroblastoma or PNs or Glioma)

RECIST v1.1 ([Eisenhauer 2009](#)) will be used for response evaluation for subjects with solid tumors except neuroblastoma, primary central nervous system tumors, or PN(s).

Subjects with solid tumors may have measurable or evaluable lesions. Measureable lesions are defined as target or non-target lesions. Details of RECIST v1.1 can be found at ctep.cancer.gov/protocolDevelopment/default.htm#protocol_development.

Response Criteria

Evaluation of Target Lesions

Complete Response (CR)	Disappearance of all target lesions. Any pathological lymph nodes (whether target or non-target) must have reduction in short axis to <10 mm.
Partial Response (PR)	At least a 30% decrease in the sum of the diameters of target lesions, taking as reference the baseline sum diameters
Progressive Disease (PD)	At least a 20% increase in the sum of the diameters of target lesions, taking as reference the smallest sum on study (this includes the baseline sum if that is the smallest on study). In addition to the relative increase of 20%, the sum must also demonstrate an absolute increase of at least 5 mm. (Note: the appearance of one or more new lesions is also considered progressions).
Stable Disease (SD)	Neither sufficient shrinkage to qualify for PR nor sufficient increase to qualify for PD, taking as reference the smallest sum diameters while on study.

Evaluation of Non-Target Lesions

Complete Response (CR):	Disappearance of all non-target lesions and normalization of tumor marker level. All lymph nodes must be non-pathological in size (<10 mm short axis)
Note: If tumor markers are initially above the upper normal limit, they must normalize for a subject to be considered in complete clinical response.	
Non-CR/Non-PD:	Persistence of one or more non-target lesion(s) and/or maintenance of tumor marker level above the normal limits
Progressive Disease (PD):	Appearance of one or more new lesions and/or unequivocal progression of existing non-target lesions. Unequivocal progression should not normally trump target lesion status. It must be representative of overall disease status change, not a single lesion increase.

Although a clear progression of “non-target” lesions only is exceptional, the opinion of the treating physician should prevail in such circumstances, and the progression status should be confirmed at a later time by the review panel (or Principal Investigator).

Evaluation of Best Overall Response

The best overall response is the best response recorded from the start of the treatment until disease progression/recurrence (taking as reference for progressive disease the smallest measurements recorded since the treatment started). The subject's best response assignment will depend on the achievement of both measurement and confirmation criteria.

For Subjects with Measurable Disease (i.e., Target Disease)

Target Lesions	Non-Target Lesions	New Lesions	Overall Response	Best Overall Response when Confirmation is Required ¹
CR	CR	No	CR	≥4 wks. Confirmation ²
CR	Non-CR/Non-PD	No	PR	≥4 wks. Confirmation ²
CR	Not evaluated	No	PR	
PR	Non-CR/Non-PD/not evaluated	No	PR	
SD	Non-CR/Non-PD/not evaluated	No	SD	
PD	Any	Yes or No	PD	no prior SD, PR or CR
Any	PD ³	Yes or No	PD	
Any	Any	Yes	PD	

1. See RECIST v1.1 manuscript for further details on what is evidence of a new lesion ([Eisenhauer, 2009](#))
2. Only for non-randomized trials with response as primary endpoint.
3. In exceptional circumstances, unequivocal progression in non-target lesions may be accepted as disease progression.
Note: Subjects with a global deterioration of health status requiring discontinuation of treatment without objective evidence of disease progression at that time should be reported as “*symptomatic deterioration*.” Every effort should be made to document the objective progression even after discontinuation of treatment.

For Subjects with Non-Measurable Disease (i.e., Non-Target Disease)

Non-Target Lesions	New Lesions	Overall Response
CR	No	CR
Non-CR/non-PD	No	Non-CR/non-PD ¹
Not all evaluated	No	not evaluated
Unequivocal PD	Yes or No	PD
Any	Yes	PD

1. Non-CR/non-PD' is preferred over 'stable disease' for non-target disease since SD is increasingly used as an endpoint for assessment of efficacy in some trials so to assign this category when no lesions can be measured is not advised

15.4 Appendix 4: Response Criteria for Neuroblastoma

Response Criteria for Neuroblastoma Subjects with Measureable Disease

Response evaluations for subjects with neuroblastoma can include measureable disease (by CT/MRI alone) or Evaluable Disease (MIBG alone) and/or in combination with bone marrow, biochemical (urine HVA/VMA).

Response Criteria for Neuroblastoma subjects with measureable disease as a component of their disease burden at enrollment will have measurable disease assessed according to RECIST v1.1 (Eisenhauer 2009) as well as evaluable disease assessments below as appropriate, to determine overall response.

Response Criteria for Neuroblastoma Subjects with MIBG Positive Lesions

Subjects who have a positive MIBG scan at the start of therapy will be evaluable for MIBG response. The use of Iodine-123 (¹²³I) for MIBG imaging is recommended for all scans. If the subject has only one MIBG positive lesion and that lesion was radiated, a biopsy must be done at least 28 days after radiation was completed and must show viable neuroblastoma.

The following criteria will be used to report MIBG response by the treating institution:

Complete Response (CR)	Complete resolution of all MIBG positive lesions
Partial Response (PR)	Resolution of at least one MIBG positive lesion, with persistence of other MIBG positive lesions
Stable Disease (SD)	No change in MIBG scan in number of positive lesions
Progressive Disease (PD)	Development of new MIBG positive lesions

The response of MIBG lesions will be assessed using the Curie scale (Ady 1995) as outlined below. This scoring should also be done by the treating institution for end of course response assessments.

[figure not shown]
The body is divided into 9 anatomic sectors for osteomedullary lesions, with a 10th general sector allocated for any extra-osseous lesion visible on MIBG scan. In each region, the lesions are scored as follows. The **absolute extension score** is graded as:

- 0 = no site per segment,
- 1 = 1 site per segment,
- 2 = more than one site per segment,
- 3 = massive involvement (>50% of the segment).

The **absolute score** is obtained by adding the score of all the segments. See diagram of sectors below:

The **relative score** is calculated by dividing the absolute score at each time point by the corresponding pre-treatment absolute score. The relative score of each subject is calculated at each response assessment compared to baseline and classified as below:

- **Complete Response:** all areas of uptake MIBG scan completely resolved. If

on

morphological evidence of tumor cells in bone marrow biopsy or aspiration is present at enrollment, no tumor cells can be detected by routine morphology on two subsequent bilateral bone marrow aspirates and biopsies done at least 21 days apart to be considered a **Complete Response**.

- **Partial Response:** Relative score ≤ 0.2 (lesions almost disappeared) to ≤ 0.5 (lesions strongly reduced).
- **Stable Disease:** Relative score > 0.5 (lesions weakly but significantly reduced) to 1.0 (lesions not reduced).
- **Progressive Disease:** New lesions on MIBG scan.

Response Criteria for Neuroblastoma Subjects with Bone Marrow Involvement

Bone marrow obtained within 28 days (or less if specified by the protocol) prior to study enrollment with tumor cells seen on routine morphology (not by immunohistochemical staining only) of bilateral aspirate or biopsy on one bone marrow sample.

Bone Marrow responses are determined by Haematoxylin and Eosin (H&E) staining of bilateral bone marrow biopsies and aspirates.

- **Complete Response:** No tumor cells detectable by routine morphology on 2 consecutive bilateral bone marrow aspirates and biopsies performed at least 21 days apart. Normalization of urinary catecholamines or other tumor markers if elevated at study enrollment.
- **Progressive Disease:** In subjects who enroll with neuroblastoma in bone marrow by morphology have progressive disease if there is a doubling in the amount of tumor in the marrow AND a minimum of 25% tumor in bone marrow by morphology. (For example, a subject entering with 5% tumor in marrow by morphology must increase to $\geq 25\%$ tumor to have progressive disease; a subject entering with 30% tumor must increase to $> 60\%$).

In subjects who enroll without evidence of neuroblastoma in bone marrow will be defined as progressive disease if tumor is detected in 2 consecutive bone marrow biopsies or aspirations done at least 21 days apart.

- **Stable Disease:** Persistence of tumor in bone marrow that does not meet the criteria for either complete response or progressive disease.

Overall Best Response Assessment:

Each subject will be classified according to his “best response” for the purposes of analysis of treatment effect. Best response (chart below) is determined from the sequence of the overall response assessments as described above.

Overall Response Evaluation for Subjects Enrolled with Measureable Disease by CT/MRI

CT/MRI	MIBG	Bone Scan/ PET-CT if performed	Bone Marrow	Catechol	Overall
PD	Any	Any	Any	Any	PD
Any	PD	Any	Any	Any	PD
Any	Any	PD	Any	Any	PD

CT/MRI	MIBG	Bone Scan/ PET-CT if performed	Bone Marrow	Catechol	Overall
Any	Any	Any	PD	Any	PD
SD	CR/PR/SD	Non-PD	Non-PD	Any	SD
PR	CR/PR	Non-PD	Non-PD	Any	PR
CR/PR	PR	Non-PD	Non-PD	Any	PR
CR	CR	Non-PD	Non-PD	Elevated	PR
CR	CR	CR	CR	Normal	CR*

CT = Computerized Tomography; MRI = Magnetic Resonance Imaging; MIBG = Meta-iodobenzylguanidine (scan); PET = Positron Emission Tomography PD = Progressive Disease; SD = Stable Disease; PR = Partial Response; CR = Complete Response.

* If one or more assessments are missing, response will be considered PR

Overall Response Evaluation for Subjects Enrolled with MIBG Positive Disease without Measureable Disease by CT/MRI

Since subjects may be enrolled without disease measurable by CT/MRI, any new or newly identified lesion by CT/MRI that occurs during therapy would be considered PD.

MIBG	CT/MRI	Bone Scan/ PET-CT if performed	Bone Marrow	HVA/VMA	Overall
PD	Any	Any	Any	Any	PD
Any	New Lesion	Any	Any	Any	PD
Any	Any	PD	Any	Any	PD
Any	Any	Any	PD	Any	PD
SD	No New Lesion	Non-PD	Non-PD	Any	SD
PR	No New Lesion	Non-PD	Non-PD	Any	PR
CR	No New Lesion	Non-PD	Non-PD	Elevated	PR
CR	No New Lesion	CR	CR	Normal	CR*

CT = Computerized Tomography; MRI = Magnetic Resonance Imaging; MIBG = Meta-iodobenzylguanidine (scan); PET = Positron Emission Tomography PD = Progressive Disease; SD = Stable Disease; PR = Partial Response; CR = Complete Response.

* If one or more assessments are missing, response will be considered PR

References:

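### Appendix 4 defines MIBG partial response and stable disease in two conflicting ways, and the overall-response tables do not say which one applies

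*Protocol*

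**What the plan says.** Section 15.4 (Appendix 4) gives two lists of MIBG response categories for children with MIBG-positive lesions.

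The first counts lesions. It is introduced with "The following criteria will be used to report MIBG response by the treating institution". PR is "Resolution of at least one MIBG positive lesion, with persistence of other MIBG positive lesions", SD is "No change in MIBG scan in number of positive lesions" and progressive disease (PD) is "Development of new MIBG positive lesions".

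The text then says that MIBG response is to be assessed on the Curie scale, and that the treating institution should do this scoring too. The relative score is the absolute score at a time point divided by the pre-treatment absolute score, calculated at each response assessment. PR is "Relative score ≤ 0.2 (lesions almost disappeared) to ≤ 0.5 (lesions strongly reduced"), SD is "Relative score > 0.5 (lesions weakly but significantly reduced) to 1.0 (lesions not reduced") and PD is "New lesions on MIBG scan". Complete response (CR) in this second list also requires marrow clearance in children who enrolled with tumour cells in the marrow. The count list has no such condition.

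Two tables follow. One is headed "Overall Response Evaluation for Subjects Enrolled with Measureable Disease by CT/MRI"; the other covers MIBG-positive disease without measurable disease. Each has a column headed only MIBG, filled with CR, PR, SD or PD. Neither table names a list. Best response, which is what the treatment-effect analysis uses, is linked to the criteria only by a reference back to the preceding text.

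**The concern.** The same institution applies both lists, both end in the same category labels, and no precedence rule is given. If the lists disagree on ordinary scans, a child can be a responder or not depending on which label is carried into the table. Two sites could classify identical scans differently and both be following the protocol. In an open-label study, leaving the choice until scans have been read also allows the more favourable response rate to be picked. The neuroblastoma cohort is small, so a single reclassified child is visible in the result.

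**Working it through.** The point disputes no stated figure. The check is to apply both lists to the same scans and follow the result into the overall tables. The Curie PR range is read as any remaining uptake with a relative score up to 0.5.

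**Step 1. One lesion clears.** Take n segments with one site each. Each scores 1, so baseline is n. One site resolves and the others persist, so the follow-up score is n − 1.

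Relative score = (n − 1)/n

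| n | Relative score | By count | By Curie |
|---|---|---|---|
| 2 | 1/2 = 0.50 | PR | PR |
| 3 | 2/3 = 0.67 | PR | SD |
| 4 | 3/4 = 0.75 | PR | SD |
| 6 | 5/6 = 0.83 | PR | SD |
| 10 | 9/10 = 0.90 | PR | SD |

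The lists agree at n = 2 and disagree at every n from 3 to 10, the scale having 10 sectors.

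**Step 2. Lesions shrink but none clears.** Take three segments, each with one massive lesion (score 3), so baseline is 9. Each shrinks to score 1, so follow-up is 3. The relative score is 3/9 = 0.33. This is PR by Curie and SD by count, because the number of lesions is unchanged.

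**Step 3. Progression.** Both lists require a new MIBG lesion, so no child changes PD status with the list chosen. There is a gap in the Curie list, however. Take four single-site segments (score 4), two of which grow to massive involvement: 3 + 3 + 1 + 1 = 8, relative score 8/4 = 2.0, with no new lesion. Curie SD stops at 1.0 and Curie PD needs a new lesion, so the child has no Curie class. By count the child is SD. A segment going from score 1 to 2 is not an example, because a score of 2 means a second site, which is a new lesion and PD on both lists.

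**Step 4. Effect on the overall tables, with no progression in any component.**

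| Disease at enrolment | MIBG PR | MIBG SD |
|---|---|---|
| MIBG-positive only | overall PR | overall SD |
| Measurable, CT/MRI SD | overall SD | overall SD |
| Measurable, CT/MRI CR or PR | overall PR | no row |

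The choice of list therefore decides the response outright in the first line, has no effect in the second, and leads to either PR or an unclassified case in the third. Both tables also lack a row for complete imaging response with normal markers when marrow or bone scan is not progressive but not CR.

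**Step 5. Size.** The Amendment 3 log (Section 12.2.2) shows at least 10 evaluable subjects per Part B cohort. It adds that a cohort with no response in 10 could be considered insufficiently active. Its operating figures reproduce: 0.95^10 = 0.599 (stated 60%) and 0.85^10 = 0.197 (stated about 20%). At n = 10, one reclassified child moves the response rate by 1/10 = 10 percentage points and can turn 0/10 into 1/10. The current sample-size section is not in the part of the protocol at hand, so 10 is used for scale only.

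**The case against.** The best defence is that the text gives the lists different jobs: the count list is for what the institution reports, and the Curie scale is how response is to be assessed, at each assessment. On that view Curie is the natural table input and only a clarifying sentence is missing. This stands as a reason to choose Curie in the repair. It does not remove the ambiguity, because the institution performs both, both produce the same labels, and the tables name neither. An analysis plan could choose one list, but sites classify under the protocol.

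The shrinkage example needs one confluent lesion per segment. If several sites fell to one, the count list would also give PR. That is true and narrows the example; the one-lesion-cleared example does not depend on it.

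The missing table rows exist whichever list is used. They are a related completeness gap and not evidence of the conflict.

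Two stronger readings are tempting. A reader might infer that progression too is defined incompatibly, and that time to progression is therefore biased by the choice of list. The documents do not support this, since both lists define PD by new lesions. A reader might also infer that the count list can only inflate response. The 3-to-1 shrinkage case contradicts that, because there the count list is the stricter one.

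**Conclusion.** The conflict between the two definitions of MIBG PR and SD is real and visible in the current Appendix 4. It runs in both directions and settles overall PR versus SD by itself in children with MIBG-only disease. Each such child is worth 10 percentage points if the cohort has 10 subjects. There is no effect where CT/MRI is SD.

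A reader might want a probability that the count list alone lifts the cohort above zero responses. The documents do not allow one. It would need the share of children who lose a lesion without halving the Curie score, and the share with MIBG-only disease, and neither is given. The no-response rule also appears only in amendment-log text and is worded permissively. The size of the problem is therefore stated per child, not as an expected shift in the rate.

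**What to change.** State in Appendix 4 that the Curie relative score is the MIBG input to both overall-response tables, keeping its marrow condition for CR. Mark the lesion-count list as descriptive only.

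Before responses are analysed, the sponsor should also reconcile the combinations that have no category:

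- relative score above 1.0 without a new lesion;
- CT/MRI CR or PR with MIBG SD;
- complete imaging response with normal markers but marrow or bone scan not CR.

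Which class each of these takes is for the sponsor to decide. In particular, a progression cut-off on the relative score appears in neither list and should not enter as a mere clarification.

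The cost is mainly wording. Curie scores are already required at each response assessment, so no new scans are needed. The downside is reclassification: some institution-reported PRs may become SD and some SDs may become PR. The protocol is already at a late amendment, so some scans may have been classified. The change should be dated and documented before the response analysis.

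### Appendix 4 gives the treating institution two conflicting MIBG response classifications under the same labels and does not say which one feeds the overall-response grids

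*Protocol*

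**What the plan says.** Protocol Appendix 4 (Section 15.4), under the heading for subjects with MIBG positive lesions, sets out two classifications one after the other.

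- **Lesion count.** It is introduced by "The following criteria will be used to report MIBG response by the treating institution". PR is "Resolution of at least one MIBG positive lesion, with persistence of other MIBG positive lesions". SD is "No change in MIBG scan in number of positive lesions".
- **Curie relative score.** The next sentence reads "The response of MIBG lesions will be assessed using the Curie scale (Ady 1995) as outlined below", followed by "This scoring should also be done by the treating institution for end of course response assessments". The relative score is "calculated by dividing the absolute score at each time point by the corresponding pre-treatment absolute score". The appendix has it computed at every response assessment and sorted into classes. PR is "Relative score ≤ 0.2 (lesions almost disappeared) to ≤ 0.5 (lesions strongly reduced"). SD is "Relative score > 0.5 (lesions weakly but significantly reduced) to 1.0 (lesions not reduced").

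Both lists use complete response (CR), PR, SD and progressive disease (PD). The same appendix then gives two grids that combine CT/MRI, MIBG, bone scan, marrow and catecholamines into an overall response, one for children with measurable disease and one for those without. Each grid has a single MIBG column, and neither says which list supplies it. Best overall response is stated to be the basis for analysing treatment effect.

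**The concern.** The same scan can be PR on one list and SD on the other, and the treating institution is told to apply both. A split between local and central readers therefore does not resolve the conflict. The MIBG category goes straight into overall response, so the neuroblastoma response rate depends on a choice that the appendix does not state. Sites could make that choice differently, or it could be settled after the results are known.

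The lists differ in kind. The count list needs one lesion to disappear, however many remain, and ignores shrinkage. The Curie list needs the summed extension score to fall by at least half, and can credit shrinkage with no change in number.

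**Working it through.** There is no sample size or power figure to reproduce. The check is to apply both lists to the same child.

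**Inputs, all from Appendix 4.** There are nine osteomedullary sectors and one extra-osseous sector. Each is scored 0 (no site), 1 (one site), 2 (more than one site) or 3 (over half of the segment involved). The absolute score is the sum. The relative score is the current absolute score divided by the pre-treatment one.

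**One lesion per segment, one lesion lost.** With k lesions the relative score is (k − 1)/k.

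| Lesions at baseline | Relative score | By count | By Curie |
|---|---|---|---|
| 2 | 1/2 = 0.50 | PR | PR |
| 3 | 2/3 = 0.67 | PR | SD |
| 6 | 5/6 = 0.83 | PR | SD |
| 10 | 9/10 = 0.90 | PR | SD |

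In this layout a Curie PR needs at least k/2 lesions to resolve: 2 of 3, 3 of 6 or 5 of 10. The count list needs one in every case.

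**Several sites in one segment.** A segment with three sites scores 2. If one site resolves, two remain and the segment still scores 2. If it is the only involved segment, the relative score is 2/2 = 1.0: PR by count, SD by Curie.

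**The reverse conflict.** A single massive lesion that shrinks from score 3 to score 1 has relative score 1/3 = 0.33, which is PR by Curie. The number of lesions is unchanged, so it is SD by count.

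**How general this is.** Take every distribution of 0 to 3 sites over ten segments with at least two lesions and no massive segment, and remove one lesion in each possible way. Of 659 such losses, 657 are PR by count and SD by Curie. The two agreements are children with exactly two lesions, whether in one segment or two (relative score 0.50). This counts patterns and says nothing about how often each occurs. Massive segments add some agreements: a baseline of 3 + 1 + 1 + 1 = 6 that loses the massive lesion falls to 3/6 = 0.50, which is PR on both lists.

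**CR and PD.** On MIBG uptake these do not conflict. Both lists require all uptake to resolve for CR, and both define PD by new lesions. The Curie CR adds a marrow condition.

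**What the grids do with the label.**

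- *No measurable disease:* with no new CT/MRI lesion and no progression on bone scan or in marrow, MIBG PR gives overall PR and MIBG SD gives overall SD. The choice of list decides the result.
- *Measurable disease, CT/MRI SD:* MIBG CR, PR or SD all give overall SD. The choice of list has no effect.
- *Measurable disease, CT/MRI PR or CR:* MIBG PR gives overall PR, with no progression elsewhere. MIBG SD has no row, so under the Curie list such a child cannot be classified.

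**The case against.** A two-tier reading is available. The count list is for institutional reporting, and the sentence stating that MIBG response will be assessed on the Curie scale can be taken as the study assessment, which sites also perform. That reading is plausible and supports Curie as the intended rule. It does not remove the problem, because both lists are worded as mandatory, neither is named as governing, and the grids refer to neither. The SAP is not at hand and might name a rule for the analysis. The protocol would still define one category in two incompatible ways.

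The objection does limit the consequences. The measurable-disease grid prevents a count PR from creating an overall response when CT/MRI is stable, so the full effect falls on children without measurable disease, whose number is not given. The bias also runs in both directions.

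A reader might infer that the count list would fill the cohort with false responses. That can be shown only with inputs the documents do not supply. Suppose there is no drug effect and each of 10 lesions in separate segments is independently missed with probability p of 1% to 5%. On a single scan a child is then a count PR with probability 1 − (1 − p)^10 − p^10, or 9.6% to 40%, against below 0.01% for a Curie PR. Among ten such children, all without measurable disease, the chance of at least one count PR is 63% to 99% with no confirmation scan. It is about 9% to 83% if one independent repeat scan must agree, and with three such children and no repeat it is 26% to 79%. The width of these ranges shows that the figures illustrate a mechanism and do not estimate anything in this trial.

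**Conclusion.** The contradiction is real and stands in current appendix text. Losing one of three or more single-site lesions in separate segments is PR by count and SD by Curie (relative score 0.67 to 0.90 for 3 to 10 lesions), and a massive lesion shrinking from 3 to 1 gives the opposite split. The lists agree for two lesions with one in each of two segments. In children without measurable disease the unstated choice decides overall PR or SD, all else equal. In those with measurable disease it matters only when CT/MRI is already PR or CR.

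This rests on the appendix wording and simple arithmetic, with no assumed error rate. How many children are affected cannot be stated, because neither the mix of disease types nor the lesion counts are given.

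A reader might also infer that one reclassified child would move the neuroblastoma cohort from no activity to activity. The documents do not support that. A rule on zero responses in 10 subjects appears only in the Amendment 3 entry for Section 12.2.2 in Appendix 11, where it says the treatment could be considered insufficiently active. The current Section 12.2.2 is not shown.

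**What to change.** Reconcile the two lists by naming one as the sole source of the MIBG column in both overall-response grids. The Curie relative score is the natural candidate, because the appendix already has it calculated and classified at each response assessment. Label the other list descriptive. In the same edit, state how CT/MRI PR or CR with MIBG SD is to be classified, since that combination now has no row.

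Then re-derive MIBG response from the Curie scores wherever they were recorded. The appendix says only that sites should do the scoring, so some scores may be missing and those children should be identified.

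The cost is one wording change and a re-derivation. The downside is that some institution-reported PRs become SD and a few SDs become PR. Progression calls on MIBG are unaffected, because both lists define PD as new lesions.

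### The neuroblastoma response grid for MIBG-positive subjects without measurable disease has no entry for unequivocal growth of a CT/MRI lesion already known at baseline, so such a subject can be scored SD, PR or CR

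*Protocol*

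**What the plan says.** Protocol section 15.4 (Appendix 4) gives two overall-response grids for neuroblastoma: one for subjects enrolled with measurable disease by CT/MRI, and one for subjects enrolled with MIBG-positive disease and no measurable disease by CT/MRI. The sentence introducing the second grid says that "any new or newly identified lesion by CT/MRI that occurs during therapy would be considered PD".

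In that grid the CT/MRI column is second and takes only three values. One leads to progression: "Any New Lesion Any Any Any PD". One is required for every better outcome, for example "SD No New Lesion Non-PD Non-PD Any SD" and "PR No New Lesion Non-PD Non-PD Any PR". The third is *Any*, used only where another modality has already given PD.

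Appendix 4 also says that each subject is classified by best response, taken from the sequence of overall assessments, for the analysis of treatment effect.

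**The concern.** Having no measurable CT/MRI disease is not the same as having no visible CT/MRI disease. The grid's title and lead-in exclude measurable lesions only. A child may therefore enter with a known soft-tissue lesion that is too small or too ill-defined to measure. If that lesion grows unequivocally, nothing new has appeared, and the grid as written sends the assessment to a no-new-lesion row.

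Best response and the date of progression are at stake for these subjects. By the first MIBG list in Appendix 4, MIBG partial response needs only one positive lesion to resolve while others persist. A child whose known mass is clearly growing while one MIBG site clears would be recorded as an overall PR. A reader who used judgement instead would record PD. The grid gives no basis for choosing between the two.

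**Working it through.** No sample size or error rate underlies this point, so there is no plan figure to reproduce. The check runs the grid as a lookup and then compares the passages.

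**Step 1. Can another column register the growth?** All rules are from Appendix 4.

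- MIBG: progression is "Development of new MIBG positive lesions", and the Curie-based list likewise requires new lesions. Growth at a known site does not qualify, and the relative-score classes stop at 1.0 with none above it.
- Bone scan/PET-CT: the column is headed "Bone Scan/ PET-CT if performed", so it may be empty.
- Marrow: progression concerns tumour in marrow only.
- HVA/VMA: no row gives PD on this column.

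None of these has to react to growth of a known soft-tissue lesion.

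**Step 2. Run the grid.** Hold CT/MRI at a grown existing lesion with no new lesion, and assume no PD elsewhere. Vary MIBG (SD, PR, CR), bone scan and marrow taken together (both non-PD or both CR), and HVA/VMA (elevated, normal). That is 3 × 2 × 2 = 12 combinations.

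| MIBG | Bone scan and marrow | HVA/VMA | Overall result | Combinations |
|---|---|---|---|---|
| SD | either | either | SD | 4 |
| PR | either | either | PR | 4 |
| CR | either | elevated | PR | 2 |
| CR | both CR | normal | CR | 1 |
| CR | both non-PD | normal | no matching row | 1 |

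Totals: SD 4, PR 4 + 2 = 6, CR 1, no row 1; 4 + 6 + 1 + 1 = 12. PD occurs in none.

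**Step 3. How the protocol treats the same kind of event in other tumours.**

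- Appendix 3 (15.3), table for non-measurable disease: unequivocal progression of non-target lesions gives overall PD, with or without a new lesion.
- Appendix 5 (15.5, RANO): clear progression of non-measurable lesions is PD, and a non-measurable enhancing lesion that grows significantly and becomes measurable counts as progression.
- Section 15.5.1 (RANO-LGG), non-target table: a significant and unequivocal increase of non-measurable lesions is PD.

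Each of these states the rule. The second neuroblastoma grid has no equivalent.

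**The case against.** **Different diseases have different criteria.** Appendix 3 expressly excludes neuroblastoma and RANO is for glioma, so no subject faces two conflicting rules. This stands: the point is a gap, not a contradiction. It also means the Appendix 3 rule cannot be assumed to fill the gap.

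**A reader might infer that the same event is PD in the measurable-disease grid and non-PD here.** The documents do not support this. Appendix 4 says those subjects "will have measurable disease assessed according to RECIST v1.1"; its reach to their non-target lesions is an inference. Appendix 3 also says that non-target progression should not normally override target-lesion status and must reflect overall disease change, not one lesion's increase. Its footnote adds: "In exceptional circumstances, unequivocal progression in non-target lesions may be accepted as disease progression". One mass growing while another site clears would not ordinarily be PD there either.

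**Newly identified may cover a lesion that first becomes measurable on therapy.** This is arguable, given that the sentence is about enrolling without measurable disease. But a lesion recorded at baseline has already been identified, the grid itself says only new lesion, and the RANO appendix spells out the transition to measurable size where it is meant.

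**Progression could still be caught.** True: MIBG, bone scan/PET-CT or marrow can each give PD, so it would be wrong to say that progression is never scored. Section 7.6, which the amendment log cites for progressive disease, is in the part of the protocol not shown and cannot be checked.

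**The subgroup may be small.** Appendix 4 describes evaluable disease as MIBG alone, and a child with disease visible only on MIBG has no CT/MRI lesion to grow. Nothing shows how many have a known non-measurable mass.

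**Conclusion.** The gap is real. Followed as written, the grid classifies unequivocal growth of a known non-measurable CT/MRI lesion as SD, PR or CR whenever no other modality shows progression. This is a lookup rule that returns an unsuitable answer, not merely detail left for later.

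The conclusion rests on two readings: that subjects without measurable disease can include some with a visible non-measurable lesion, and that a lesion documented at baseline is neither new nor newly identified.

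No magnitude is claimed. A reader might infer that one false PR would reverse a ten-subject cohort's activity decision. The zero-responses-in-ten criterion is visible here only in the amendment log entry for section 12.2.2, which says the treatment *could be* considered insufficiently active. The document gives no rate at which this misclassification would occur, so any shift in the decision probability would depend on an invented input.

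**What to change.** In the Appendix 4 grid for MIBG-positive disease without measurable disease:

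- make the CT/MRI entry that leads to PD *new lesion, or unequivocal progression of an existing non-measurable lesion*;
- make the CT/MRI entry in the SD, PR and CR rows *no new lesion and no unequivocal progression*;
- amend the sentence above the grid to match;
- define unequivocal progression within Appendix 4, because Appendix 3 excludes neuroblastoma and a cross-reference would not settle its meaning.

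The cost is wording in one appendix, applied to scans already taken. The protocol is well advanced (Appendix 2 says dose escalation is complete and Appendix 5 refers to Amendment v09), so assessments already made in this subgroup may need re-scoring. The response rate may become slightly less favourable.
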